Statistical analysis	
Data processing and statistical analysis will be carried out by the service provider, Axonal-Biostatem.
 
The statistical analyses will be described in a Statistical Analysis Plan (SAP) validated by the Sponsor and the Scientific Committee, prior to the freeze-in.
 
Statistical analyses will be performed after baseline freezing of the data with SAS® software (SAS Institute, NC, Cary, USA), version 9.4 or later.
 
Demographic and efficacy/performance analyses will be performed in the ITT population. The primary endpoint will be analyzed in PP (Per Protocol) and then validated in the ITT (intention to treat) population. The safety analyses will be performed in the safety population.
 
For quantitative variables, the usual statistics (n, missing n, mean, standard deviation (SD), median, first and third quartiles (Q1 and Q3), minimum and maximum) will be presented. IC95% may be

	
presented if relevant (especially for the primary endpoint).
 
For categorical variables, the usual statistics (n, missing n, frequency and percentage) for each modality will be provided.
 
Descriptive statistics will be provided in aggregate and by pump group.
 
The type 1 error, α, is set at 5% when the tests used will be two-sided (superiority) and α will be set at 2.5% when the tests will be one-sided in the case of Noninferiority (IC95%).
 
Analysis of the main objective
 
The non-inferiority analysis will be produced via an Ancova or mixed model on the Per-Protocol population and then on an intention-to-treat basis.
 
If non-inferiority is demonstrated, a superiority analysis will be conducted.
 
Analysis of secondary objectives
 
The secondary criteria will be described and then be the subject of mixed or Ancova models.
 
A non-inferiority analysis on HbA1c data and superiority analyses on Time in range, number of glycemic events, patient satisfaction will be performed.

Regulatory framework	ID-RCB number, CPP opinion, CNIL MR001 and RGPD compliance, information to the ANSM, approval of investigator contracts by the CNOM, transparency obligations
Logistics	CRO Axonal-Biostatem (Nanterre, France)

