10.2 SECONDARY ENDPOINTS

The secondary endpoints were:

❖ HbA1c:

- Value measured in the laboratory from a blood sample taken before the D0 visit and just before the 3-month visit

❖ Glucose Level Measurements

- Average Glucose Measurements over each period and over the entire study duration
- Minimum and maximum values
- Time in range expressed as a % (see ADA and International Consensus on Time in Range recommendations^{25,26})

These values are automatically calculated by the FreeStyle Libre software and will be reported by the investigator.

❖ Glycemic events

- Number of symptomatic and non-symptomatic hypoglycemic episodes during the evaluation period, broken down by severity level (see below)

- Number of symptomatic and non-symptomatic hyperglycemia events during the evaluation period, broken down by severity level (see below)

This information is derived from the FreeStyle Libre data and the data entered by the patient in the PDM.

The definition of hypoglycemia and hyperglycemia is the ADA consensus definition²⁵ :

Outcome	Definition
Hypoglycemia	Level 1: glucose <70 mg/dL (3.9 mmol/L) and glucose \geq 54 mg/dL (3.0 mmol/L) Level 2: glucose <54 mg/dL (3.0 mmol/L) Level 3: a severe event characterized by altered mental and/or physical status requiring assistance
Hyperglycemia	Level 1—elevated glucose: glucose >180 mg/dL (10 mmol/L) and glucose \leq 250 mg/dL (13.9 mmol/L) Level 2—very elevated glucose: glucose >250 mg/dL (13.9 mmol/L)
Time in range	Percentage of readings in the range of 70–180 mg/dL (3.9–10.0 mmol/L) per unit of time

❖ Device tolerance

- Local skin tolerance at the pump site (adhesive hold) and at the FreeStyle Libre blood glucose sensor site (adhesive hold).
- Any local or systemic safety issues should be reported during the study, including the additional one-month phase at the end of the study for patients in the "OmniPod" group

❖ Incidents with devices

- Any type of incident involving the operation of the medical devices used, particularly for pumps: removal, control problems, transmission difficulties, obstructions, leaks, etc.

❖ Patient satisfaction

- Self-questionnaire evaluating satisfaction with the use of the device (pump+PDM)
- Final question regarding patient preference between the Medtrum device and the Insulet device

❖ Insulin treatment

- The insulin treatment used should be documented
- Delivered insulin doses will be derived from the pump's data logging

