11.2.4 Analysis of the effectiveness / performance of the device

Analysis of primary efficacy endpoint:

The non-inferiority analysis of the primary efficacy endpoint will be performed with an ANOVA, with the DM as an explanatory variable, on the *per protocol* population and then on the *intention-to-treat* population. If the upper bound of the IC95% of the Omnipod-Medtrum estimated difference in means (LSmeans) exceeds the non-inferiority bound, it will be rejected.

Non-inferiority bounds are defined in this protocol and will be used in the statistical analysis plan.

If non-inferiority is demonstrated, a superiority analysis will be conducted.

Secondary efficacy endpoint analyses:

The secondary efficacy endpoints will be analyzed for the variables listed below.

Each variable will be described globally and by pump group.

In case of non-inferiority analysis, the same methodology as for the primary endpoint will be used.

In case of comparison of quantitative variables, parametric (T-test) or non-parametric (Mann-Whitney) tests of comparison of means will be used. In case of comparison of qualitative variables, CHI² or Fisher exact tests will be used.

In case of tests on changes within each group, paired data tests will be used (paired data T-test or Wilcoxon signed ranks test, depending on the distribution of the data).

❖ **HbA1c:**

- Evolution of the value measured in the laboratory from a blood sample taken before the D0 visit and just before the 3-month visit
- Description in the total population, in each group and comparison between groups.

❖ **Glucose measurements**

- Average of glucose measurements over each period and over the entire study duration
- Description of the minimum and maximum values over the total duration of the study
- Description of the % of Time in Range (see ADA and International Consensus on Time in Range recommendations^{25,26})
- Description in the total population, in each group and comparison between groups.

❖ **Glycemic events**

- Description of the number of symptomatic and non-symptomatic hypoglycemic events during the evaluation period, broken down by severity level (see ADA consensus definitions²⁵)
- Description of the number of symptomatic and non-symptomatic hyperglycemia events during the evaluation period, broken down by severity level (see ADA consensus definitions²⁵)
- Description in the total population, in each group and comparison between groups.
-

❖ **Device tolerance**

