4.4.2 Secondary endpoints

The secondary endpoints were:

- HbA1c:
 - Value measured in the laboratory from a blood sample taken before the D0 visit and just before the 3-month visit
- Glucose Level Measurements
 - Average of glucose measurements over each time period and over the entire study duration
 - Minimum and maximum values
 - Time in range expressed as a %.

These values were automatically calculated by the FreeStyle Libre software and will be reported by the investigator.

- Glycemic events
 - Number of symptomatic and non-symptomatic hypoglycemic events during the evaluation period, broken down by severity level
 - Number of symptomatic and non-symptomatic hyperglycemia events over the evaluation period, broken down by severity level

This information was derived from the Free Freestyle data and the data entered by the patient in the MDP.

The definition of hypoglycemia and hyperglycemia is the ADA consensus definition:

Table 1—Summary of consensus definitions			
Outcome	Definition		
Hypoglycemia	Level 1: glucose <70 mg/dL (3.9 mmol/L) and glucose \geq 54 mg/dL (3.0 mmol/L) Level 2: glucose <54 mg/dL (3.0 mmol/L) Level 3: a severe event characterized by altered mental and/or physical status requiring assistance		
Hyperglycemia	Level 1—elevated glucose: glucose $>$ 180 mg/dL (10 mmol/L) and glucose \leq 250 mg/dL (13.9 mmol/L) Level 2—very elevated glucose: glucose $>$ 250 mg/dL (13.9 mmol/L)		
Time in range	Percentage of readings in the range of 70–180 mg/dL (3.9–10.0 mmol/L) per unit of time		

- Device tolerance
 - Local skin tolerance at the pump site (adhesive hold) and at the FreeStyle Libre blood glucose sensor site (adhesive hold)
 - Any local or systemic safety issues were to be reported during the study, including the additional one-month phase at the end of the study for patients in the Omnipod group
- Incidents with devices
 - Any type of incident involving the operation of the medical devices used, especially for pumps: pulling out, control problems, transmission difficulties, occlusion, leakage, etc.
- Patient satisfaction
 - Self-questionnaire evaluating satisfaction with the use of the device (pump + PDM)

- Final question regarding patient preference between the Medtrum device and the Insulet device
- Insulin treatment
 - The insulin treatment used should be documented

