6 MODIFICATIONS TO THE ANALYSES PROVIDED FOR IN THE PROTOCOL

Not applicable

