7.4.2 Secondary endpoint analyses

Analyses will be performed on the ITTm population.

Each variable will be described globally and by pump group.

The secondary endpoints are:

1. HbA1c

The evolution of HbA1c (measured in the laboratory) between D0 and 3M will be described, and a comparison between the groups will be made using a Student's t test or a Mann and Whitney test.

2. Glucose level measurement

The mean blood glucose level and its standard deviation (Blood Glucose Deviation SD) will be described over each period (between V1 and V2, then between V2 and v3, then between V3 and V4) and over the total duration of the study (mean, median, standard deviation, Q1-Q3, minimum and maximum). The coefficient of variation of glucose values will also be described.

The evolution of the average blood glucose level compared to baseline will be described at each visit.

FSL wear time (%) will be described.

The % of blood glucose values spent in target (time in range: [70; 180]), hypoglycemia (<70mg/dl), and hyperglycemia (>180 mg/dl) will be described over each time period in each pump group and in the total population.

For these criteria, comparisons between groups will be made using the Student or Mann-Whitney test.

3. Glycemic events

The number of hypoglycemic events will be described overall and in each period by severity level (according to ADA consensus definitions) overall and in each pump group.

Comparisons between groups will be made using Student or Mann-Whitney tests.

The % of time spent in hyperglycemia will be described overall and over each period and in each pump group. Comparisons between groups will be made using Student's t test or Mann and Whitney test.

4. Device tolerance

The analysis of this criterion is detailed in section 7.4 of this document.

5. Incidents with devices

The following criteria will be described for each period and by pump group (after reclassification):

- Pump occlusion (yes; no)
 - If yes, number of times
- Pump detachment (yes; no)
 - If yes, number of times
- Complete stop / breakage of the pump (yes; no)
 - If yes, number of times
- Other pump malfunction (yes; no)
 - All other possible malfunctions will be listed.

6. Patient satisfaction

The following criteria will be described for each period and by pump group:

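### SAP 7.4.2 gives no analysis of hyperglycaemic events by severity level, although SAP 4.4.2 keeps that endpoint and protocol 11.2.4 plans a comparison, so no planned measure isolates Level 2 (>250 mg/dL)

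*SAP*

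**What the plan says.** **Protocol.** Section 10.2 lists as a secondary endpoint: "Number of symptomatic and non-symptomatic hyperglycemia events during the evaluation period, broken down by severity level". The definitions table there sets Level 1 at above 180 and up to 250 mg/dL, and Level 2 at above 250 mg/dL. Section 11.2.4, under glycaemic events, plans: "Description of the number of symptomatic and non-symptomatic hyperglycemia events during the evaluation period, broken down by severity level". Under the same heading it adds: "Description in the total population, in each group and comparison between groups". The statistical analysis row of the protocol summary goes further: "superiority analyses on Time in range, number of glycemic events, patient satisfaction will be performed".

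**SAP endpoint list.** Section 4.4.2 repeats the endpoint, "Number of symptomatic and non-symptomatic hyperglycemia events over the evaluation period, broken down by severity level", and reprints the same definitions.

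**SAP analysis.** Section 7.4.2 item 3 describes the number of hypoglycaemic events by ADA level, overall and by period, with a Student or Mann-Whitney comparison. For hyperglycaemia the item reads: "The % of time spent in hyperglycemia will be described overall and over each period and in each pump group". A group comparison of that percentage follows. The sentence gives no threshold; item 2 of the section defines hyperglycaemia as above 180 mg/dL.

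**Declared changes.** SAP section 6, on modifications to the protocol's analyses, reads: "Not applicable".

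**The concern.** The SAP names an endpoint in one section and gives it no analysis in the section where analyses are specified. In its place stands a different quantity: a percentage of time instead of a count of events, and one pooled band instead of two levels. A statistician programming from 7.4.2 would produce no table of hyperglycaemic events and nothing specific to glucose above 250 mg/dL.

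Two things are at stake. First, a comparison planned in the protocol goes missing without a declared change, so a reader of the report could not tell a deliberate decision from an oversight. Second, Level 2 is the more severe hyperglycaemia band in the documents' own definitions, and the protocol introduction names hyperglycaemia with ketoacidosis among the acute emergencies that insulin therapy is meant to prevent. In a comparison of two insulin delivery devices, that band deserves the result the protocol promised.

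**Working it through.** The plan states no figure on this point, so the check is a comparison of texts, followed by an illustration of what the pooled measure can and cannot show.

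**1. Endpoint against analysis**

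| Element | Protocol 10.2 / 11.2.4 | SAP 4.4.2 | SAP 7.4.2 |
|---|---|---|---|
| Hypoglycaemic events by level | endpoint; described; compared | endpoint | counted by level; compared |
| Hyperglycaemic events by level | endpoint; described; compared | endpoint | no count, no level |
| Hyperglycaemia cut-offs | 180 and 250 mg/dL | 180 and 250 mg/dL | 180 mg/dL only |

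The comparison between groups comes from protocol 11.2.4 (and, for the number of glycaemic events, the protocol summary). Protocol 10.2 and SAP 4.4.2 only list and define the endpoint.

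**2. Search of the other SAP sections.** The derived variables (4.4.3), baseline sensor list (7.3), remaining secondary analyses (7.4.2 items 4 to 7) and tolerance analyses (7.5) contain no count of hyperglycaemic events and no variable with a 250 mg/dL cut-off. The baseline list has a number of hypoglycaemias and time above 180 mg/dL, but no hyperglycaemia count.

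**3. What equal time above 180 mg/dL leaves open.** Assume, purely for illustration, that glucose is lognormal; the documents do not say so. Let p be the fraction of time above 180 and CV the coefficient of variation. Then σ = √ln(1 + CV²), μ = ln 180 − z(1−p)·σ, and time above 250 = 1 − Φ((ln 250 − μ)/σ).

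| Time above 180 | CV 25% | CV 30% | CV 36% | CV 42% |
|---|---|---|---|---|
| 30% | 3.2% | 5.0% | 7.1% | 9.0% |
| 35% | 4.3% | 6.6% | 9.2% | 11.5% |
| 40% | 5.6% | 8.5% | 11.6% | 14.3% |

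With time above 180 fixed at 35%, time above 250 runs from 4.3% to 11.5%. Equal results on the SAP's hyperglycaemia measure do not imply equal Level 2 exposure.

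**4. What the other item 2 measures would show.** Take two hypothetical arms, both with 35% of time above 180, one with 5% and the other with 12% above 250 (ratio 12/5 = 2.4). Under the same model, σ = ln(250/180) / (z for time above 250 − z for time above 180):

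- 5% arm: σ = 0.3285 / (1.645 − 0.385) = 0.261; CV = √(e^σ² − 1) ≈ 27%
- 12% arm: σ = 0.3285 / (1.175 − 0.385) = 0.416; CV ≈ 43%

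With μ = ln 180 − 0.385σ, the mean e^(μ + σ²/2) is about 168 and 167 mg/dL, so the SD (CV × mean) is about 45 and 73 mg/dL. Time below 70, Φ((ln 70 − μ)/σ), is about 0.06% and 3.0%.

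Mean glucose and time above 180 would therefore look alike, while SD, CV and time below 70 would differ clearly. Those measures would signal wider dispersion without saying how much of it lay above 250 mg/dL.

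**The case against.** **The arms would not look the same.** A reader might infer that two arms differing only in Level 2 exposure would give identical results under 7.4.2. They would not: item 2 also reports mean glucose, SD, CV and time below 70 mg/dL and plans group comparisons, and step 4 shows that several of these would move. What stands is narrower: none of them isolates Level 2, and none is the endpoint listed.

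**The endpoint has not been removed.** A reader might infer that the SAP deletes it or that it will certainly go unreported. SAP 4.4.2 still contains it, and protocol 11.2.3 says that all collected variables will be described and/or listed. That could yield a listing or a description, but not the comparison in protocol 11.2.4. The defect is an endpoint without a specified analysis.

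**Delivery failures are covered elsewhere.** It is tempting to argue that the pooled measure hides occlusions. The documents do not support that. Item 5 counts occlusions, detachments and complete stops by period and group. The protocol's occlusion rationale contrasts conventional catheter pumps with patch pumps, and both pumps here are patch pumps. The documents do not present Level 2 hyperglycaemia as the marker of pump failure. Equally, item 5 records the incident and not its glycaemic consequence. Adverse event reporting is only a partial substitute, because protocol 13.2.1 keeps events unrelated to the device or its procedure out of the eCRF.

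**The data may not be there.** This carries weight. Protocol 7.4 and 7.5 have V2 and V3 collect time-stamped glucose values and hyperglycaemic events. However, sites transcribe software-calculated values into the eCRF (protocol 3.4.3 and 10.2), neither sponsor nor CRO can open the device applications (9.1), and the SAP baseline list has no such field. Availability is uncertain, for the event counts as well as for time above 250.

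**Conclusion.** The point holds as an undeclared inconsistency, both within the SAP and between the SAP and the protocol. Hyperglycaemic events by severity level remain a listed secondary endpoint with a comparison planned in the protocol, but 7.4.2 substitutes a pooled percentage of time and SAP 6 reports no change. As written, the pumps are never compared on Level 2 hyperglycaemia.

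The scope is one secondary endpoint, and the primary non-inferiority analysis is untouched. The conclusion rests on the text alone. The lognormal figures show only that time above 180 mg/dL does not determine time above 250 mg/dL; the 35%, 5% and 12% are hypothetical values, not estimates for this trial. The correction should be made before database freeze.

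**What to change.** In SAP 7.4.2 item 3, add the number of Level 1 and of Level 2 hyperglycaemic events per patient, described by period and randomised group, with the same between-group comparison as for hypoglycaemic events, using the event data collected at V2 and V3. The comparison can run only to V3, because only Omnipod-arm patients have a V4. Keep the percentage of time above 180 mg/dL, state that cut-off in item 3, and add the percentage of time above 250 mg/dL where the sensor report or eCRF provides it.

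First check whether the eCRF holds the counts. If it does not and they cannot be re-extracted, replace the entry in SAP 6 with a declared and justified removal of this endpoint's analysis, so that 4.4.2 and 7.4.2 can be reconciled.

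The cost is SAP wording and a few extra tables if the data are in the eCRF, plus some re-extraction by the sites if they are not.

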- Description of local skin tolerance at the pump site and at the FreeStyle Libre blood glucose sensor site).
- Description of any local or systemic safety issues reported during the study, including the additional one-month phase at the end of the study for patients in the "Omnipod" arm
- Description in the total population, in each group and comparison between groups of the number of patients who had at least one tolerance problem.

❖ **Incidents with devices**

- Description of any type of incident involving the operation of the medical devices used, particularly for pumps: pulling out, control problems, transmission difficulties, obstructions, leaks, etc.
- Description in each group, in the overall population and comparison between groups

❖ Patient satisfaction

- Description of the responses to the self-questionnaire assessing satisfaction with the use of the device (pump+PDM), in each group and in the total population
- Comparison of responses between groups
- Description of responses to the final question regarding patient preference between the Medtrum device and the Omnipod device: in each group and in the total population

❖ Insulin treatment

- Description of insulin doses delivered
- Description of any additional insulin injections with a pen during the study
- Description in the total population, in each group and comparison between groups

11.2.5 Tolerance analyses:

The analyses will be performed on the tolerance population.

Prior to any analysis all DM-related incidents and DM-related tolerance will be coded by the MedDRA regulatory medical dictionary (version 20.0 or later).

A summary table (number and percentage of patients with an AE and number of events) by organ system class (OSG) and preferred term (PT) will be presented for the following categories of events by dissociating DM-related incidents and tolerance:

- According to the link (device AND procedure),
- Depending on the link (device OR procedure),
- Depending on the severity,
- Depending on the actions taken (de-pairing).

A listing of individual data will be provided describing all the information collected via the eCRF concerning the IS (including duration, resolution, severity criteria, linkage, severity etc.)

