- Responses to the Medtrum A7+ and Omnipod pump satisfaction questionnaires. Comparisons between pump groups of responses will be made using Student's t test or Mann and Whitney test if relevant or applicable.
- Answers to the specific questionnaire related to preference

7. Insulin treatment

The following criteria will be described for each period and per pump group, comparisons between groups will be made using Student's or Mann and Whitney test:

- Total dose administered daily (sum Basal + Bolus)
- Average Daily Basal Dose
- Average daily bolus dose
- Number of Boluses/day

The evolution of these criteria in relation to the baseline will be described at each stage.

Additional insulin injections with a pen during the study will be listed.

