7.5 ANALYSIS OF TOLERANCE DURING THE STUDY

Analyses will be performed overall and by pump group on the **tolerance population**. Prior to any analysis, all DM-related incidents and DM-related tolerance will be coded by the MedDRA regulatory medical dictionary (version 20.0 or later).

The number of patients who had at least one tolerance problem will be described. The following criteria will be described for each period and by pump group:

- Irritation/itching (yes; no)
 - If yes, maximum intensity (low; moderate; intense)
- Redness (yes; no)
 - If yes, maximum intensity (low; moderate; intense)
- Other adverse events (yes; no)
 - All other events related to tolerance will be given in a listing.

A summary table (number and percentage of patients with AEs and number of events) by organ system class (OSG) and preferred term (PT) will be presented for the following categories of events by dissociating incidents and tolerance related to the medical device:

- According to the link (device AND procedure)
- According to the link (device OR procedure)
- Depending on the severity
- Depending on the actions taken (de-boosting)

A listing of individual data will be provided describing all the information collected via the eCRF concerning the AE (including duration, resolution, severity criteria, linkage, severity etc.)

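### The SAP prespecifies no between-arm comparison of device incidents or of patients with a tolerance problem, although the protocol plans both and SAP section 6 declares no change

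*SAP*

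**What the plan says.** **Protocol.** In section 11.2.4, the entry on incidents with devices asks for: "Description in each group, in the overall population and comparison between groups". The entry on device tolerance asks for: "Description in the total population, in each group and comparison between groups of the number of patients who had at least one tolerance problem". The same section gives the method: "In case of comparison of qualitative variables, CHI² or Fisher exact tests will be used".

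**SAP.** Section 7.4.2 item 5 (incidents with devices) says: "The following criteria will be described for each period and by pump group (after reclassification". It then lists pump occlusion, detachment, complete stop or breakage, and other malfunction. Section 7.5 (tolerance) says: "The number of patients who had at least one tolerance problem will be described". Neither place mentions a comparison, a difference or a test.

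Elsewhere the SAP does state comparisons. Laboratory HbA1c, glucose measures, glycaemic events and satisfaction each have a sentence naming Student's t or Mann-Whitney. For insulin treatment, which includes the number of boluses per day: "comparisons between groups will be made using Student's or Mann and Whitney test".

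SAP section 6, which exists to record departures from the protocol's analyses, reads: "Not applicable".

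**The concern.** This trial compares one patch pump with another. Occlusion, detachment, breakage and skin reactions are the outcomes closest to the device itself. Estimated HbA1c is further away: protocol 6.3 leaves investigators free to manage diabetes as usual, so insulin can be adjusted during follow-up. Similar glucose control therefore does not by itself show similar device reliability.

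With counts per arm and no interval on the difference, readers must judge for themselves how much difference the data can exclude. In a trial of about 100 patients, similar-looking counts are easily taken as evidence of similarity. A comparison chosen after the data are seen would also lack the standing of one prespecified before the database freeze. Separately, section 6 tells the reader that the SAP carries out the protocol's analyses, which is not so for these two endpoints.

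**Working it through.** **1. The texts side by side**

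| Endpoint | Protocol 11.2.4 | SAP |
|---|---|---|
| Device incidents | Describe and compare groups | 7.4.2 item 5: describe by period and pump group |
| Patients with at least one tolerance problem | Describe and compare groups | 7.5: describe |
| Test for qualitative variables | Chi-square or Fisher | None named in the SAP |
| Change declared | - | Section 6: none |

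The SAP already derives the binary variable that the protocol wants compared. AL_PBTOL_D in section 4.4.3 is 1 if the patient reported irritation or itching, redness, or another adverse event during follow-up. The comparison is therefore feasible but not written down.

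**2. Does another part of the SAP supply it?** Section 5.2 allows two-sided 95% CIs for categorical data where judged appropriate. The categorical table template in section 8 has two group columns and a p-value column. Both are generic: neither names a test, requires a between-arm difference, or is tied to these endpoints. The template for events by SOC and PT has only a Total column. Reporting a comparison is permitted but not prespecified.

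**3. What a restored comparison could show.** The documents give no event rates for these endpoints, so the rates below are assumptions.

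- Patients per arm: SAP 5.1 reports 100 included, with 1:1 allocation. Section 7.4.2 uses the ITTm population, which excludes 4 patients (section 7.1.3), leaving at most 96. An even split gives 100/2 = 50 or 96/2 = 48 per arm. The even split is assumed.
- Power is the sum, over all pairs of event counts (i, j), of P(i)·P(j) where the two-sided Fisher p-value is below 0.05, with i and j binomial.

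| Assumed rates | Power, n = 48 per arm | Power, n = 50 per arm |
|---|---|---|
| 10% vs 20% | 0.18 | 0.19 |
| 10% vs 30% | 0.61 | 0.64 |
| 5% vs 25% | 0.72 | 0.75 |
| 10% vs 35% | 0.80 | 0.82 |

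- 95% CI half-width for the difference when both arms have rate p: 1.96·√(2p(1−p)/n). With n = 50 and p = 0.10: 1.96·√(0.18/50) = 1.96 × 0.060 = 0.118, about 12 points. With p = 0.20: 1.96·√(0.32/50) = 1.96 × 0.080 = 0.157, about 16 points.

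Only large differences would be detected reliably. A non-significant test would say little, whereas the interval states how large a difference remains compatible with the data.

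**4. Which period.** SAP item 5 reports each period. After V3, Omnipod-arm patients may use the Medtrum pump for a month (protocol 7.5 and 7.6). Events between V3 and V4 in that arm can therefore arise on the Medtrum pump, so a randomised comparison has to stop at V3.

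**The case against.** The strongest defence is that the protocol is not of one mind. Protocol 4.2 says that the secondary objectives are to describe, and it mentions a comparison between arms only for satisfaction. The protocol summary names superiority analyses for time in range, glycaemic events and satisfaction, not for incidents or tolerance, although it also says in general terms that secondary criteria will be modelled. Protocol 11.2.5, the dedicated tolerance section, is descriptive. The SAP can be read as following that strand, and describing safety data without tests is a legitimate choice. This stands as an argument for description, but not as an answer to section 6. Protocol 11.2.4 is the detailed analysis section and states both comparisons explicitly, so leaving them out is a change to record.

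Three stronger readings are tempting, and the documents do not support them:

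- A reader might infer that the arms are never compared on these endpoints. Results are reported by pump group, and sections 5.2 and 8 leave room for intervals and p-values. What is missing is prespecification.
- A reader might infer that leaks, control problems and transmission faults disappear into a yes/no item because item 5 has no rows for them. SAP 7.5 codes all device-related incidents in MedDRA and tabulates them by SOC and PT, with analyses overall and by pump group. Protocol 10.2 lists those faults as examples only and requires no separate rows.
- A reader might take the power figures to show that well-powered tests were lost. They rest on assumed rates, and power is about 0.18-0.19 for 10% versus 20%.

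**Conclusion.** The point holds as a discrepancy between protocol and SAP. Two between-group comparisons planned in protocol 11.2.4 are not prespecified in the SAP, no categorical test is named to carry them out, and section 6 is wrong to declare no modification.

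The consequence is moderate. The primary analysis, its alpha and the sample size are untouched, and the endpoints are secondary and already tabulated by arm. What is lost is a prespecified estimate of the difference, with its uncertainty, on the outcomes most directly tied to the pump. This conclusion rests on the text alone. The power and interval figures depend on assumed event rates and an even split of 96 to 100 patients, and serve only to show that the CI should be the main output.

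**What to change.** 1. **SAP 7.4.2 item 5.** For D0 to V3 only, report for each category the SAP already defines (occlusion, detachment, complete stop or breakage, other malfunction) the proportion of patients with at least one event by arm, the Medtrum minus Omnipod difference, its 95% CI, and a chi-square or Fisher test.
2. **SAP 7.5.** Do the same for any tolerance problem, using AL_PBTOL_D restricted to D0 to V3. Keep the V3 to V4 month descriptive.
3. **Labelling.** State that these are secondary comparisons without multiplicity control and that the interval is the main result.
4. **Alternative.** If the sponsor prefers description only, replace the entry in section 6 with a statement of that change and the reason.
5. **Tidying.** Item 4 of SAP 7.4.2 refers the reader to section 7.4 for tolerance, which is in 7.5. The SOC/PT template should have group columns to match the text of 7.5.

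The cost is a few sentences, some extra table columns and five more secondary p-values (four incident categories plus one tolerance variable). It needs only the patient-level indicators, by period, that the SAP already plans to tabulate.
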